8.0 CALCULATIONS

- 8.1 The following formula will be used to calculate the number of viable bacteria recovered:

$$\text{Log10} \left\{ \frac{A + B + C}{3} \right\}$$

Where: A, B, and C = Individual Plate Counts

- 8.2 If colonies on one of the plates are uncountable, the count(s) from the remaining plate(s) will be used.

9.0 STATISTICS

- 9.1 After calculating the \log_{10} populations recovered from Tests D, B, and A, these will be statistically compared to the Initial Population Test C (Control) using a One-Way Analysis of Variance (ANOVA) with Dunnett Multiple Comparisons with the Control. All statistical calculations will be performed using the 0.05 level of significance for Type I (α) error.
- 9.2 Prior to comparing Phases to the Initial Population (Control), the 30-minute evaluation of the Initial Population should be shown to be statistically equivalent to the “time-zero” Initial Population of the microorganism. Hypotheses are:

H_0 : Initial Population = Test Phase, or

H_A : Initial Population \neq Test Phase.

- 9.3 If $p \leq 0.05$ for each comparison to the control, H_0 will be rejected and the Test Phase will be considered to be significantly different from the Initial Population. There is potential for low variance of the data, which would result in rejecting H_0 . The difference between the Initial Population and the Test Phase will also be used to confirm significant differences. If the difference is greater than or equal to 0.20, the two tests will be determined to be significantly different. Differences less than 0.20 between the two tests will be determined to be not significantly different.
- 9.4 The Product Efficacy evaluation is effective if the antimicrobial test product produces a significant reduction in the population of the microorganism.
- 9.5 The Neutralizing/Recovery Medium Inhibition Evaluations are considered non-inhibitory if all recovered populations are not statistically different from the Initial Population of the microorganism.
- 9.6 The Diluent Broth Inhibition Evaluation is considered non-inhibitory if all recovered populations are not statistically different from the Initial Population of the microorganism.
- 9.7 Neutralization is considered adequate if all recovery populations are not statistically different from the Initial Population.

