- 7.8 Immediately prior to initiating the neutralization assay, an inoculum suspension will be prepared in Phosphate Buffer Saline (PBS) solution from each culture on an agar plate, and the concentrations adjusted to approximately 3.0×10^8 to 1.0×10^9 CFU/mL. The suspensions will then be serially diluted in PBS to achieve an inoculum titer of approximately 3.0×10^3 to 1.0×10^4 CFU/mL, and used as test inoculum for each species.

Inoculum Assay (Initial Population) – Test C

- 7.9 Test Inoculum will be assayed by adding a 0.1 mL aliquot of the inoculum to 5.0 mL of PBS solution (IP), vortexing for at least 3 seconds, and immediately (within 1 minute) pour-plating, in triplicate, 1 mL aliquots of the test material with TSA. This assay will be performed three additional times for a total of four replicates.
- 7.10 The diluted test inoculum suspensions will be allowed to stand for at least 30 minutes, following which, 1 mL aliquots will be pour-plated, in triplicate, with TSA.

Product Efficacy Evaluation (*In Vitro*) – Test D

- 7.11 This phase of the neutralization assay determines whether the antimicrobial test material is able to reduce the population of the challenge microorganism. This assay will be performed in four replicates.
- 7.12 To each of four test tubes containing 5.0 mL of each test material, a 0.1 mL aliquot of the test inoculum will be added. The suspensions will be vortexed for at least 3 seconds and, immediately (within 1 minute), 1 mL aliquots of each replicate will be pour-plated, in triplicate, with TSA.
- 7.13 The tubes will be allowed to stand for at least 30 minutes, following which 1 mL aliquots of each replicate will be pour-plated, in triplicate, with TSA.

Neutralizing/Recovery Medium Inhibition Evaluations (*In Vitro*) – Test B

- 7.14 This phase of the neutralization assay assures that the sterile Stripping Suspending Fluid with product neutralizers (SSF++) the sampling solution employed in the

evaluation, is not inherently toxic to the microorganism. This assay will be performed in four replicates.

- 7.15 To each of four test tubes containing 5.0 mL of one of the sampling solutions, a 0.1 mL aliquot of the test inoculum will be added. The suspensions will be vortexed for at least 3 seconds and, immediately (within 1 minute), 1 mL aliquots of each replicate will be pour-plated, in triplicate, with Tryptic Soy Agar with product neutralizers (TSA+).

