- 7.16 The tubes will be allowed to stand for at least 30 minutes, following which 1 mL aliquots of each replicate will be pour-plated, in triplicate, with TSA+.

Diluent Broth Inhibition Evaluation (*In Vitro*) – Test B

- 7.17 This phase of the neutralization assay assures that the Butterfield's Phosphate Buffer Solution with product neutralizers (BBP++) employed in the evaluation is not inherently toxic to the microorganism. This assay will be performed in four replicates.
- 7.18 Four test tubes containing 5.0 mL of diluent broth to be used in the test will be prepared, and a 0.1 mL aliquot of the test inoculum will be transferred to each tube. The suspension will be vortexed for at least 3 seconds, and immediately (within 1 minute), 1 mL aliquots of each replicate will be pour-plated, in triplicate, with TSA+.
- 7.19 The tubes will be allowed to stand for at least 30 minutes, following which, 1 mL aliquots of each replicate will be pour-plated, in triplicate, with TSA+.

Neutralizer Efficacy Evaluation (*In Vivo*) – Test A

- 7.20 This phase of the evaluation determines whether the neutralizing method chosen effectively eliminates the antimicrobial activity of the test materials.
- 7.21 Prior to sampling, the subjects will be questioned regarding adherence to the protocol. Subjects will also be examined physically to ensure no evidence of injury, dermatosis, or dermatitis is present at the sampling sites. Female subjects will be required to provide a urine sample for a pregnancy test. Only those female subjects with a negative test will be allowed to proceed into testing.
- 7.22 A 1.5" x 5" test area will be demarcated on each side of the abdomen. After the test areas are marked, each area will be processed using three 70% isopropyl alcohol swabs for a total of ~ 90 seconds (~ 30 seconds each), followed by an air-dry for at least 1 minute. This step will prepare the skin for the neutralization test.
- 7.23 A test material (reference Section 9.4.2 of the Study Protocol) will be applied to a 1.5" x 5" site on the abdomen of the subjects following the instructions for inguinal application in Appendix 2, with the randomly assigned test material.
- 7.24 The site will then be sampled using the Cylinder Sampling Technique 30 seconds + 5 seconds (30 seconds to 35 seconds) post product-application completion.

- 7.25 The Cylinder Sampling Technique will be performed as described in Section 9.4.7 of the Study Protocol (using SSF++).

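### Neutralizer efficacy (Appendix 4, Test A) is judged only against a control in a different fluid and agar, so carry-over above the 0.20 log10 limit can pass if the neutralizing media recover more organisms than PBS and plain TSA

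*Combined protocol and SAP*

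**What the plan says.** All references are to Appendix 4 of the combined protocol and SAP.

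- **Test C (Initial Population), 7.9.** The control is made by "adding a 0.1 mL aliquot of the inoculum to 5.0 mL of PBS solution (IP"), and the agar is plain: "1 mL aliquots of the test material with TSA". Neither the fluid nor the agar contains neutralizers.
- **Test B (SSF++), 7.14 to 7.16.** Inoculum goes into product-free SSF++, and aliquots "will be pour-plated, in triplicate, with Tryptic Soy Agar with product neutralizers (TSA"+), immediately and after at least 30 minutes. Its stated purpose is to show that the sampling fluid is not toxic.
- **Test A, 7.20 to 7.27.** This phase "determines whether the neutralizing method chosen effectively eliminates the antimicrobial activity of the test materials". A cylinder sample is taken in SSF++ from treated skin, adjusted to 5.0 mL, inoculated, and plated in TSA+ at the same two holding times.
- **Comparator, 9.1.** For Tests D, B and A, "these will be statistically compared to the Initial Population Test C (Control) using a One-Way Analysis of Variance (ANOVA") and Dunnett's procedure. No contrast between A and B is planned.
- **Decision rule, 9.3.** A difference below 0.20 log10 counts as no difference; 0.20 or more counts as a difference.
- **Pass criteria, 9.5 and 9.7.** Test B passes if it does not differ from Test C. For Test A: "Neutralization is considered adequate if all recovery populations are not statistically different from the Initial Population".

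**The concern.** Test A has to answer one question: once the sample is in the tube, does residual product go on killing? Test A differs from Test C in three ways: the fluid (SSF++ against PBS), the agar (TSA+ against TSA), and the presence of product and skin sample. Only the third bears on the question. The SSF++ Test B shares Test A's fluid and agar, so A minus B removes the first two. The plan produces this matched control at both holding times, then uses it only as a toxicity check.

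If the neutralizing fluid and agar recover somewhat more organisms than PBS and plain TSA, that gain offsets real kill in the tube and Test A can look adequate. Kill after sampling would then lower the post-treatment recoveries in the main study and be read as product effect on skin.

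**Working it through.** **The plan's own figure.** At least 18 subjects with two sites each give 36 samples. Over 3 materials and 3 species, 36 / 9 = 4 samples per cell, which matches the stated minimum of four. Tests B and C are also run in four replicates.

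**What the written checks bound.** Write A, B and C for mean log10 recoveries at one holding time. Then

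A − B = (A − C) − (B − C).

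The plan requires |A − C| < 0.20 and |B − C| < 0.20, so |A − B| is held only below 0.40. As loss of organisms: 1 − 10^(−0.20) = 37%; 1 − 10^(−0.30) = 50%; 1 − 10^(−0.40) = 60%.

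The largest observed carry-over (B − A) that still passes is just under 0.20 + (B − C):

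| B − C | Largest B − A that passes |
|---|---|
| −0.15 | 0.05 |
| 0 | 0.20 |
| +0.05 | 0.25 |
| +0.10 | 0.30 |
| +0.15 | 0.35 |
| +0.19 | 0.39 |

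**Chance of passing: one material, one species, one holding time.** Assumptions not in the documents: replicate SD 0.10 log10 in each test, normal errors, true carry-over 0.30. The standard error of a difference of two means is 0.10 × √(2/4) = 0.0707. A versus C alone passes with probability Φ((offset − 0.10)/0.0707), which is 8%, 24%, 50% and 76% at offsets of 0, +0.05, +0.10 and +0.15. Requiring B versus C as well, with the same Test C mean in both comparisons (by simulation), gives:

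| True offset B − C | Written rule (A vs C and B vs C) | A vs B limit of 0.20 |
|---|---|---|
| 0 | 8% | 8% |
| +0.05 | 23% | 8% |
| +0.10 | 43% | 8% |
| +0.15 | 54% | 8% |

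With SD 0.06 and offset +0.10 the two rules pass 49% and 1%. A second simulation used triplicate Poisson plates at about 107 CFU, the geometric middle of the 59 to 196 CFU per plate implied by 0.1 mL of a 3.0 × 10^3 to 1.0 × 10^4 CFU/mL inoculum in a total of 5.1 mL, plus a range of extra variance. At offset +0.10 the written rule passes about 49%; with A versus B added, 0% to 11%.

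**Replace or add?** Take the mirror case: medium loss of 0.15 (B below C) and carry-over of 0.15, a total loss of 0.30.

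| Rule | SD 0.10 | SD 0.06 |
|---|---|---|
| Written rule (A vs C, B vs C) | 8% | 1% |
| A vs B in place of A vs C (B vs C kept) | 54% | 76% |

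With all three checks at SD 0.10, the +0.10 offset case with carry-over 0.30 falls from 43% to 7%, and the mirror case stays at 7%.

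**Price of the added check.** At zero offset, SD 0.10 and true carry-over of only 0.10, the chance of passing falls from 92% to 86%.

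**The case against.** The strongest reply is that the gap opens in one direction only. SSF++/TSA+ must recover more than PBS/TSA, and the documents give no figure to suggest that it does. Test B is described as a toxicity check, so the direction the authors had in mind is B below C, where comparison with C is stricter than 0.20. At zero offset the two rules perform alike. All this stands, and makes the concern conditional. It does not remove it, because 9.3 and 9.5 would accept a positive offset of up to 0.20 without comment.

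Other replies stand in part:

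- Section 9.2 requires the 30-minute Initial Population to be equivalent to time zero. That limits die-off in PBS as a reason for C to read low. It does not address a difference in recovery already present at immediate plating.
- Section 9.7 requires all recovery populations to pass. If the same carry-over and offset applied to three species independently, 43% would become 0.43³ ≈ 8%, and 0.43⁶ < 1% over three species and two times. The tabulated rates describe a problem confined to one species and one time.
- Test A also contains skin material and any flora left after the alcohol preparation in 7.22, so A minus B is not pure product carry-over.
- The cited ASTM method and in-house SOP may prescribe the Test C comparison. That cannot be checked from the documents.

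A reader might infer that carry-over is unbounded if the difference in 9.3 is taken as a signed loss. The documents do not support this: 9.2 states a two-sided alternative and 9.3 speaks of the difference between two tests.

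**Conclusion.** The point holds as a conditional weakness in the assay validation. The comparator for neutralizer efficacy is not matched on fluid and agar, although a matched one is generated. If the neutralizing media recover more than PBS and plain TSA, carry-over above the plan's own 0.20 limit can pass. An offset of +0.05 takes the pass rate for a 0.30 log10 carry-over from 8% to 23%, and +0.10 takes it to 43%, for one species and one time. These rates rest on an assumed SD of 0.10 and an assumed offset, and they fall when all species and times must pass.

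Two stronger conclusions are tempting and are not supported:

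- That carry-over of almost 0.40 log10 will pass. This is the extreme corner, with B nearly 0.20 above C and A nearly 0.20 below it. It also bounds observed means, not true kill.
- That the non-inferiority result is biased by a stated amount. Only carry-over that differs between materials would shift that comparison. All three materials list the same active ingredients at the same concentrations, and Test Product #2 and the control share the 5.1 mL volume. Volume and applicator do differ across the materials, so equal carry-over is not assured, but the documents give no basis for a figure.

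**What to change.** In Appendix 4, 9.1 and 9.7, keep A versus C and B versus C as they are, and add a third requirement: for each material and species, the Test A mean must differ from the product-free SSF++ Test B mean by less than 0.20 log10 at the same holding time (immediate and 30 minutes). Name the SSF++ Test B explicitly, because the diluent check in 7.17 to 7.19 is also labelled Test B. Where feasible, run that Test B from the same inoculum preparation as Test A.

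Do not substitute A versus B for A versus C. That would let medium toxicity and carry-over each approach 0.20 and together lose almost 0.40 against the initial population.

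Cost: mainly wording, since both tests are already planned at both times, and no extra subjects. If Test A needs several sessions, some Test B plates would be repeated. The chance of failing an adequate neutralizer rises slightly, as shown in the working. The added check does not separate product from skin material or residual flora. Because A versus C is kept, it also does not rescue a sound neutralizer whose media recover less than PBS and plain TSA.
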